#### 4 Data sources

- CRF data, frozen on from the June 27, 2020 transfer.
- Meropenem AST data from the central lab transferred via Box on November 4, 2021, updated on May 13, 2022.
- WGS data from Meridian Hackensack transferred on December 2, 2021.
- AST panel from China was data 31 March 2022.
- AST panel from US central lab was dated 07 April 2022.

#### 5 Report Components

- Inclusion/Exclusion reasons
- Enrollment by region
- Enrollment by region/site

The following tables will be summarized with the following sets of column variables:

- Geographic region
- Geographic region, limited to infections
- Infection vs colonization (non-infection)
- Presence of a carbapenemase
- Presence of a carbapenemase, limited to infections
- Central Meropenem MIC levels
- Central Meropenem MIC levels, limited to infections
- Clonal Group 2 vs other clonal groups
- Clonal Group 2 vs other clonal groups, limited to infections

##### 5.1 Tables

Variables to be summarized:

- Baseline and Admission characteristics
  - Gender
  - Age (continuous and categorical)
  - Race
  - Ethnicity
  - Origin location (all origins + hove vs all others)

- ICU admission prior to first positive culture
- Charlson comorbidity index
- Comorbidities
  - Diabetes
  - Coronary artery disease
  - Congestive heart failure
  - Heart disease
  - Peripheral vascular disease
  - Cerebrovascular disease
  - Dementia
  - Connective tissue disease
  - Peptic ulcer disease
  - Hemiplegia
  - Chronic kidney disease
  - Severe chronic kidney disease
  - Any chronic renal replacement therapy
  - Renal dysfunction
  - Liver disease
  - Cirrhosis
  - Cirrhosis and history of variceal bleeding
  - Cirrhosis and portal hypertension
  - Hepatitis B infection
  - Hepatitis C infection
  - Chronic obstructive pulmonary disease
  - History of malignancy
  - Immunocompromised
  - Solid organ transplant
  - Recent or current chemotherapy
  - Stem cell transplant
  - TNF-alpha blocker in the last month
  - HIV with AIDS diagnosis
  - Other monoclonal antibody in last month
  - Prednisone 10 mg/day or equivalent
- Culture information
  - WGS species
  - CRF species
  - Variables from CRFs
    - Infection/colonization
    - Culture anatomic source
    - Infection/colonization by source
    - Days from admission to culture (continuous)
    - $\geq 2$  days from admission to culture
    - Healthcare associated/non-hospital acquired (CRACKLE II analysis definition)
    - Pitt score (continuous)
    - Pitt score  $< 4/\geq 4$
    - Patient location at first positive culture
    - Did other pathogen from the same source grow? (polymicrobial)
  - Meropenem MIC via central lab

- Molecular results
  - Carbapenemase present (yes/no)
  - Specific carbapenemase present
  - Clonal group
  - Capsular polysaccharide locus (KL)
  - Lipooligosaccharide outer core locus (OCL)
- Central AST results (limited to those run by both labs China/US)
  - Amikacin
  - Cefepime
  - Ceftazidime
  - Ceftriaxone
  - Ciprofloxacin
  - Imipenem
  - Levofloxacin
  - Meropenem
  - Piperacillin tazobactam
  - Polymixin B/Colistin
- CRF Susceptibility results (S//R and S/NS)
  - Amikacin
  - Ampicillin-sulbactam
  - Cefepime
  - Ceftazidime
  - Ceftriaxone
  - Ciprofloxacin
  - Colistin
  - Doripenem
  - Fosfomicin
  - Gentamicin
  - Imipenem
  - Levofloxacin
  - Meropenem
  - Piperacillin-tazobactam
  - Polymyxin B
  - Tobramycin
  - Trimethoprim-sulfamethoxazole
- Outcomes
  - Days from culture to discharge/death
  - Days from admission to discharge/death
  - Disposition after discharge
  - 30 day all-cause mortality
  - 90 day all-cause mortality
  - 30 day DOOR outcomes
  - DOOR outcome components
    - Unsuccessful discharge
    - No clinical response
    - Renal failure or *C. difficile*
  - 30 day clinical response

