### 3 Statistical Methods

#### 3.1 General considerations

- Global tests of statistically significant differences across any of the regions are provided. For pairwise comparisons between regions, USA will be the reference group.
- Tables are summarized by region, infection/colonization, meropenem MIC levels, presence of carbapenemase, and Clonal Group 2 vs other clonal groups.
- Categorical variables are tested using the chi-square test. Continuous variables and ordered categorical variables are compared using the Kruskal Wallis test.
- The Miettinen-Nurminen (score) method is used to calculate the confidence interval (CI) of the difference in proportions.
  - Please note that the only censoring is administrative censoring at 30 days. As this is an observational study with information collected from the medical record, unless subjects are known to have died, they are considered to be alive.
- Modeling will be limited to subjects with an infection.
- DOOR probabilities are calculated using Halperin CI.
- IPW adjustment for DOOR probability and difference in proportions will be utilized.
- Logistic regression is performed with study site as random effect.
- Analyses will be summarized for all subjects and repeated for the subset of subjects with an infection.
- Throughout this report we consider  $p < 0.05$  with a two-sided test to be statistically significant.

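### Central susceptibility results from a China and a US laboratory are pooled and tested by region with no laboratory variable; if isolates were tested by region of origin, a China-USA difference cannot be told apart from a laboratory difference.

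*SAP*

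**What the plan says.** SAP section 4 lists two multi-drug susceptibility files: "AST panel from China was data 31 March 2022" and "AST panel from US central lab was dated 07 April 2022". It also lists a separate transfer for one drug, from a laboratory named in the singular: "Meropenem AST data from the central lab transferred via Box on November 4, 2021, updated on May 13, 2022".

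SAP section 5.1 merges the two panels under "Central AST results (limited to those run by both labs China/US") and names ten agents beneath. One row is "Polymixin B/Colistin", although the local (CRF) susceptibility list in the same section gives those two drugs separate rows.

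SAP section 5 states "The following tables will be summarized with the following sets of column variables", and geographic region heads that list. SAP section 3.1 adds "Global tests of statistically significant differences across any of the regions are provided" and "For pairwise comparisons between regions, USA will be the reference group". The tests are chi-square for categorical variables and Kruskal-Wallis for continuous and ordered ones, two-sided at 0.05, with no laboratory term.

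On where isolates were tested, protocol section 6.1 says only that they go to central research laboratories, in the plural. Neither document gives the allocation of isolates to laboratories, a common test method or breakpoint set for central testing, a subset tested in both places, or a concordance check.

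**The concern.** Central testing normally removes the variation between local laboratories, so that regions can be compared on one scale. Here the central result comes from two laboratories, and one of them is located in one of the regions being compared. Restricting the table to agents that both laboratories ran aligns the drug list. It does not align panel concentration ranges, reading or calibration.

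Susceptibility of the index strains is a secondary objective (SAP 2.4.2). SAP 2.3 expects strain microbiology to differ by region, and region is an a priori comparison (SAP 2.2). A laboratory offset would therefore look like the finding that the study expects, and nothing in the plan would reveal it. The global test has the same problem whenever China is one of the regions in it.

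**Working it through.** The documents give no figure on this point, so there is nothing to reproduce. The check has three steps.

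**1. Can region and laboratory be separated?** Take a model with an intercept and indicators for China region, other region and China laboratory. If each region's isolates go to one laboratory only (China to China, all others to the US), the distinct rows are:

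- USA: (1, 0, 0, 0)
- China: (1, 1, 0, 1)
- Other: (1, 0, 1, 0)

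The China-region and China-laboratory columns are identical, so the rank is 3 for 4 parameters. No analysis of the central data alone can separate the two effects. If isolates from the same region were tested at both laboratories, the rank is 4 of 4 and they can be separated. The conclusion therefore depends on the allocation, which the documents do not give.

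**2. Size when the laboratories differ by a fixed number of percentage points.** Assumed, not from the documents: equal true resistance p in both regions, n isolates per region, and one laboratory reading b lower, so q = p - b. With m = (p + q)/2,

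P(p-value < 0.05) ≈ Φ[(b - 1.96·SE0)/SE1], where SE0 = √(2m(1-m)/n) and SE1 = √((p(1-p) + q(1-q))/n).

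For p = 0.85, b = 0.05, n = 200: SE0 = √(2 × 0.825 × 0.175/200) = 0.0380, SE1 = √((0.1275 + 0.16)/200) = 0.0379, and Φ[(0.05 - 0.0745)/0.0379] = Φ(-0.65) = 26%. For b = 0.02 it is 8%, and for b = 0.10 it is 71%. Simulation gives 5.1% at b = 0. Over p from 50% to 95% and n from 100 to 400, the ranges are about 5-22% (b = 2 points), 11-77% (b = 5) and 29-100% (b = 10).

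**3. Size when the laboratories differ by a fraction of a dilution.** Assumed: log2 MIC normal with SD 2, rounded up to whole dilutions, 100 versus 200 isolates, identical strains, one laboratory offset by d dilutions. If half the isolates are resistant, the apparent gap is Φ(d/2) - 0.5, which is 5, 10 and 19 points for d = 0.25, 0.5 and 1. At 95% resistant it is only about 1 to 8 points. Repeated simulation runs gave these shares with p < 0.05:

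| Test and setting | d = 0.25 | d = 0.5 | d = 1 |
|---|---|---|---|
| Kruskal-Wallis, uncapped MICs | 16-19% | 50-52% | 97-98% |
| Chi-square, 50% resistant | 13-14% | 37-40% | 89-91% |
| Chi-square, 95% resistant | 5-9% | 8-21% | 25-67% |

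The spread in the last row reflects mainly the direction of the offset: an offset that lowers MICs does more harm than one that raises them. The Kruskal-Wallis row assumes that the panel does not cap the MICs. With a panel top one dilution above the cut-off, 95% resistance and a downward offset, it falls to about 9%, 19% and 67%.

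Steps 2 and 3 do not conflict. A given gap in percentage points is easier to detect at 95% resistance, but a given dilution offset produces a much smaller gap there.

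**The case against.** The strongest reply is that the allocation is unknown. A reader might infer from the two files that Chinese isolates were tested only in China and US isolates only in the US, and so that region and laboratory are certainly aliased. The documents do not state this. The phrase about both laboratories could even mean isolates tested twice, which would remove the problem. This stands as a limit on the claim. The ten-drug list and the combined polymyxin row make a restriction on drugs the likelier meaning, and the wording of the China file suggests testing by origin, but neither proves it.

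Second, meropenem may be unaffected. It has its own transfer from a single unnamed central laboratory, so if that laboratory tested every isolate, the comparisons based on that transfer are not confounded. This stands too.

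Third, analysed isolates must be carbapenem-resistant locally and meropenem-resistant centrally (SAP 2.5), so many agents may sit far from a cut-off, and every offset used above is assumed. The SAP also does not say whether the multi-drug rows hold MICs or categories. This reduces the likely size but does not remove the mechanism.

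Fourth, a reader might infer that future site selection or the mortality findings are undermined. Appendix II, Aim 1 ties site selection to incidence, and protocol 7.2 ties likely response to novel drugs to strain data and resistance mechanism. None of the weighting or regression models in SAP 5.2 contains a susceptibility result. The stronger reading is not supported.

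What the reply leaves standing is that the SAP tests pooled two-laboratory data by region without stating the allocation or planning any check.

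**Conclusion.** The point holds in conditional form and should be corrected. As written, the SAP allows a laboratory difference to be reported as a statistically significant regional difference in central susceptibility. If laboratory follows region, the China-USA contrast cannot be rescued by adjustment. If it does not, the allocation still has to be stated and used.

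The size cannot be fixed from the documents. Under the assumptions above, inflation is large for agents with MICs near a cut-off. For percent resistant it is much smaller where nearly all isolates are resistant, although a full-dilution downward offset still matters there. Local CRF susceptibility cannot settle the question, because local laboratories also vary with region.

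The effect is confined to part of one secondary objective. The primary 30-day mortality objective and the DOOR analyses could be touched only through the exclusion of isolates not meropenem-resistant on central testing (SAP 2.5) and the grouping by central meropenem MIC (SAP 5), and only if both laboratories supplied those meropenem data.

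**What to change.** In SAP sections 3.1 and 5.1:

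- State which isolates each laboratory tested and by what method, and add a testing-laboratory variable to the central susceptibility rows.
- Apply one breakpoint set to both panels. Where MICs are pooled, truncate them to the concentration range that both panels cover.
- Where laboratory and region coincide, confine global and pairwise p-values to regions tested in the same laboratory. Show the China-USA contrast descriptively, with the laboratory labelled.
- If any isolates were tested in both laboratories, report concordance and keep the contrast with that caveat.
- State the source of the central meropenem MIC, and apply the same rule to it only if both laboratories supplied it.

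The cost is SAP wording and one extra column or stratum, with no new testing. The China-USA p-value for these rows is given up where laboratory and region coincide.

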## 5.2 Outcome analyses

The difference in proportion in 30- and 90 day mortality will be summarized with confidence intervals. The IPW difference in proportion, with 95% CI, will also be summarized. Pairwise DOOR probabilities and 95% CI will be estimated using Halperin's method. Both an unadjusted and IPW adjusted DOOR probability with 95% CI will be estimated. IPW models for infection vs. non-infection comparisons included:

- Geographic region
- Immunocompromising conditions
- Preadmission location (home origin vs other)
- Age-adjusted Charlson comorbidity index

IPW models for regional comparisons (infections only) included:

- Anatomical source of infection
- Immunocompromising conditions
- Preadmission location (home origin vs other)
- Age-adjusted Charlson comorbidity index

Post hoc, a logistic regression model was used to explore risk factors for mortality. Variables included in the analysis were:

- Geographic region (USA as reference)
- Anatomical source of infection (blood as reference)
- Aged-adjusted Charlson comorbidity index
- Immunocompromising conditions
- Pre-admission location
- Monomicrobial vs polymicrobial culture
- Acquired carbapenemase gene
- Clonal group (CG2 as reference)
- Capsular polysaccharide locus (KL)
- Lipooligosaccharide outer core locus (OCL)
- Site (random effect)

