### 6.3 Clinical Definitions

**MDRO:** Specific Multi-Drug Resistant Organisms of interest are defined in the Appendices

**Culture episode:** A positive MDRO culture from any anatomical site marks the beginning of a culture episode that includes any subsequent cultures within 7 days from the same site and during the same hospital admission. If a period of more than 7 days elapses between positive cultures, this is considered the start of a new culture episode. A positive MDRO culture from a different anatomical site is considered a separate culture episode.

**Hospital Setting:** For the purposes of this protocol, patients are considered to be in a hospital setting during the first positive MDRO culture if they are admitted to a short-term acute care hospital, or if they are in the emergency department awaiting admission with a subsequent admission. In addition, a stay in the emergency department of >24

hours will qualify as a hospital setting.

**Infection:** A patient is deemed to have an infection if a MDRO is isolated from blood or any other sterile source. For patients with positive respiratory cultures the criteria outlined by the American Thoracic Society (ATS) and the Infectious Diseases Society of America (IDSA) are used (6, 7). For patients with positive cultures from urine or surgical wounds, the CDC/National Healthcare Safety Network (NHSN) criteria are used (8). Patients with cultures from non-surgical wounds are considered infected only if the treating physician documents infection in the medical record and evidence of systemic inflammation on the day the positive culture is documented, defined as an abnormal systemic white cell count (either >10K cells/uL or <4K cells/uL), and/or abnormal body temperature (either >99.5 °F or <96 °F).

**Colonization:** All culture episodes that do not meet the preceding definitions of infection are designated as colonization (9).

**Renal failure:** Renal failure will be defined using the Risk, Injury and Failure components of the Risk, Injury, Failure, Loss of kidney function, and End-stage kidney disease RIFLE criteria (10).

**Severity of acute illness:** The Pitt bacteremia score (PBS) is calculated using temperature, mental status, cardiac arrest, blood pressure, mechanical ventilation, as described (11).

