### 2.2 *A priori* and *Post Hoc* Analyses

The following comparisons were defined *a priori*:

- Geographic region
- Geographic region, limited to infections
- Infection vs colonization (non-infection)
- Presence of a carbapenemase
- Presence of a carbapenemase, limited to infections
- Modeling

- DOOR probability
- Inverse probability weighted (IPW) DOOR probability

The following comparisons were *post-hoc*:

- Central Meropenem MIC levels
- Central Meropenem MIC levels, limited to infections
- Clonal Group 2 vs other clonal groups
- Clonal Group 2 vs other clonal groups, limited to infections
- Modeling
  - Logistic regression model with site as random effect

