### 2.3 Hypotheses

CRAB infection is associated with significant morbidity and mortality, including in comparison with CRAB colonization (non-infection). Specific patient characteristics and clinical outcomes, and molecular and microbiological of the strains, will differ across regions, information which will aid in the design of randomized clinical trials on therapeutics and diagnostics for CRAB infections.

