#### 3.2 Outcome measure definitions

**Carbapenem susceptibility:** a culture is included if it has a corresponding susceptibility form with documented resistance at the local lab to at least one carbapenem (meropenem, imipenem, doripenem).

**Infection vs. colonization (non-infection):** only cultures that meet the study surveillance definition of infected are counted as infected. For CRAB, respiratory isolates are considered to be infected if the respiratory diagnosis on the CRF was tracheobronchitis, pneumonia, no mechanical ventilation, ventilator-associated pneumonia, or an “other” diagnosis identified by 2 study investigators ([name] and [name]). All other cultures, including cultures missing information needed for the assignment of infection/colonization (non-infection), are considered to be colonized (not infected).

**30-day mortality:** an admission is considered alive at 30 days if they are not recorded as dead. If an admission is discharged alive and there is no other information on the 90-day form or if they have a discharge date but no disposition, then they are assumed to be alive.

**90-day mortality:** an admission is considered alive at 90 days if they are not recorded as dead. If an admission is discharged alive and there is no other information on the 90-day form or if they have a discharge date but no disposition, then they are assumed to be alive.

**DOOR:** The DOOR variable reported in MDRO studies is an ordered categorical variable measuring status at 30 days following the culture collection date. The categories are:

- Clinical Response at 30 days, with no events
  - Symptomatic response, no anti-CRAB antibiotic, no relapse
- 1 event
- 2 or 3 events
- Death

The possible events are:

- No clinical response at 30 days
- “Bad” discharge within 30 days or readmitted within 30 days
- Renal failure post-culture or *C. difficile* infection.

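### The weighted infection vs colonization contrast omits culture source, so it mixes a non-sterile-source comparison with sterile-source infections that have no colonized counterpart

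*SAP*

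**What the plan says.** Protocol 6.3 (Clinical Definitions) settles infection status by source for part of the cohort: "A patient is deemed to have an infection if a MDRO is isolated from blood or any other sterile source". The remainder rule is equally plain: "All culture episodes that do not meet the preceding definitions of infection are designated as colonization". Respiratory, urine, surgical-wound and non-surgical-wound cultures each have their own criteria.

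SAP 3.2 carries this forward: "only cultures that meet the study surveillance definition of infected are counted as infected". It adds a CRAB-specific rule for respiratory isolates only.

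Infection vs colonization is one of the comparisons that SAP 2.2 lists as a priori, and SAP 2.3 includes it in the hypothesis. SAP 5.2 plans differences in 30-day and 90-day mortality and a DOOR probability, unadjusted and weighted. The covariate list headed "IPW models for infection vs. non-infection comparisons included" has geographic region, immunocompromising conditions, preadmission location and age-adjusted Charlson index. The list headed "IPW models for regional comparisons (infections only) included" has anatomical source in place of region. The post hoc logistic model for mortality also has source, with blood as the reference.

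SAP 5.1 tabulates infection status by source. No outcome contrast between infection and colonization is planned within any source or set of sources.

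**The concern.** Weighting is meant to make infected and colonized patients comparable on what predicts outcome. The SAP evidently regards source as relevant to outcome, since it enters the regional weighting model and the mortality model. In this contrast source is not balanced, and for blood and other sterile sites it cannot be: the definition leaves no colonized patient to stand in for them.

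There is a second, separate gap. Respiratory, urine and wound cultures can fall on either side, but by different criteria, so the chance of being labelled infected can vary by source. If mortality also varies by source, leaving it out confounds the comparison even where both states occur.

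At stake is how the adjusted figure can be used. The study exists to inform trial design. For a non-sterile culture, separating infection from colonization is a real classification question; for blood the definition has answered it. A pooled adjusted figure does not tell a trial designer what the difference is in the sources where the question is open.

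**Working it through.** The documents give no effect size, power or precision for this comparison, so there is no figure to reproduce. Three checks were made.

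**1. Definitions against covariates.** From Protocol 6.3 and SAP 3.2, P(infected | sterile source) = 1, so the sterile share of the colonized group is 0. From SAP 5.2, source is not in the model. The regional weighting and the logistic model do contain source but use infected patients only, so neither fills the gap.

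**2. Crude decomposition for mortality.** Let f be the sterile share of infections, m_s and m_n the mortality of sterile and non-sterile infections, and m_c the mortality of colonized patients.

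All-source difference = f·m_s + (1 − f)·m_n − m_c = (m_n − m_c) + f·(m_s − m_n)

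The first term is the non-sterile difference and the second is the shift. The inputs are not in the documents. The values below are assumptions within the 16%–58% range for 30-day mortality in Protocol Appendix II, Background.

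| f | m_s | m_n | m_c | All-source difference | Non-sterile difference | Shift (points) |
|---|---|---|---|---|---|---|
| 20% | 45% | 25% | 25% | 29 − 25 = 4 | 0 | +4 |
| 20% | 45% | 25% | 20% | 29 − 20 = 9 | 5 | +4 |
| 30% | 45% | 25% | 20% | 31 − 20 = 11 | 5 | +6 |
| 20% | 37% | 37% | 16% | 37 − 16 = 21 | 21 | 0 |
| 20% | 25% | 37% | 16% | 34.6 − 16 = 18.6 | 21 | −2.4 |

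For f from 10% to 40%, the shift runs from +2 to +8 points at m_s = 45% and m_n = 25%, and from −1.2 to −4.8 at m_s = 25% and m_n = 37%. At the ends of the range (58% and 16%) it runs from +4.2 to +16.8.

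**3. Does weighting change this?** A simulation of 1,000,000 patients used assumed inputs:
- Source: blood 15%, respiratory 55%, urine 15%, wound 15%.
- One binary comorbidity, prevalence 40%, included in the weighting model.
- Infection probability: 1 for blood; 0.5, 0.3 and 0.4 for the other sources, plus 0.1 with the comorbidity.
- Mortality: 15%, plus 10 points with the comorbidity, plus 20 points for blood.

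Blood then makes up 27% of infections.

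| Infection effect set in non-sterile sources | Weighted, no source | Source added, whole cohort | Non-sterile only, source added |
|---|---|---|---|
| 0 points | +5.4 | +3.0 | +0.1 |
| 8 points | 11.3 | 10.0 | 8.1 |

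The first column agrees with the decomposition: 0.27 × 20 = 5.4 when the non-sterile effect is 0, and 8 + 0.27 × (20 − 8) = 11.2 when it is 8. The middle column does not recover the non-sterile effect, because the propensity is 1 for blood and no colonized patient can be weighted to represent it. Restriction with source in the model does recover it.

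**The case against.** The strongest reply is that bacteraemia belongs to the exposure. The protocol defines infection to include it, so its mortality should count in an infection vs colonization contrast, and +4 points in the first row of the table is the correct crude difference for infection as defined. This stands. The all-source contrast is a valid description of a composite, and the comparison within non-sterile sources is a different quantity that the SAP did not set out to estimate.

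It also stands that omitting source from the whole-cohort model is defensible, since including it breaks positivity. The regional model is no direct precedent: it compares regions among infected patients, where source does not fix the exposure.

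A reader might infer from SAP 2.3 that the plan treats the contrast as the excess mortality attributable to infection. The wording there is of association only, and the contrast is not among the objectives in SAP 2.4.1 and 2.4.2, which describe infections. A reader might also infer that the planned figure is biased upward. The documents give neither the sterile share nor mortality by source, so they support no direction.

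Finally, the tables in SAP 5.1 will show that blood occurs only among infections. That reveals the imbalance but does not give the outcome difference in the remaining sources. Nor does the objection deal with source left unadjusted among non-sterile cultures.

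**Conclusion.** The point holds as a limit on interpretation and a gap that is cheap to close. The weighted infection vs colonization estimates for 30-day mortality, 90-day mortality and DOOR describe a composite that includes sterile-source infections with no colonized counterpart. They also leave source unadjusted among non-sterile cultures.

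Relative to the non-sterile comparison, the crude mortality shift is f × (m_s − m_n). It is +4 points at an assumed 20% sterile share and 20-point gap, zero if mortality is equal, and negative if sterile-source mortality is lower. The planned output would not show which case applies.

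Two stronger readings are not supported. The first is that the all-source contrast is computed wrongly; it is correct for infection as the protocol defines it. The second is that comparing source between infected and colonized patients is circular throughout; only the sterile categories are fixed by definition, and differences among the others are informative. The primary objective, 30-day mortality of CRAB infections, is untouched.

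**What to change.** In SAP 5.2:

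- Keep the all-source contrast and state that it includes sterile-source infections by definition, with no colonized patients from those sources.
- Add the same contrasts for 30-day mortality, 90-day mortality and DOOR, restricted to sources where both states occur: respiratory, urine, wound, and any abdominal or other cultures (categories in Protocol 7.2) that are not sterile-site. Put source in that weighting model, and show respiratory alone.
- Describe the outcomes of sterile-source infections separately, without a colonization comparator.
- Limit any test of source by infection status to the non-sterile categories.

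The cost is SAP wording and some added analysis on data already collected: three outcomes in two source sets give six further weighted estimates, plus one description. The restricted contrasts will be less precise because sterile-source infections drop out of them. The SAP should label these analyses as added after the a priori list.

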## **5 Study Population**

All patients who are admitted to one of the participating hospitals and who have a CRAB isolated in a clinical culture will be included.

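### The a priori infection vs colonization contrast is weighted for region and patient covariates but not for site, so it can be biased if hospitals' infection share and mortality are correlated within region.

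*SAP*

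**What the plan says.** SAP 2.2 lists infection vs colonization among the comparisons defined a priori, and the hypothesis in SAP 2.3 refers to it. SAP 5.2 gives the weights: under "IPW models for infection vs. non-infection comparisons included" stand region, immunocompromising conditions, preadmission location (home or other) and the age-adjusted Charlson index. These weights serve the mortality differences at 30 and 90 days and the DOOR probability.

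Site enters one model. SAP 3.1 says "Logistic regression is performed with study site as random effect", and SAP 5.2 describes that model: "Post hoc, a logistic regression model was used to explore risk factors for mortality". Infection status is not among its variables, and SAP 3.1 adds "Modeling will be limited to subjects with an infection". It therefore cannot adjust the infection vs colonization contrast.

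Both groups can arise in one hospital, because Appendix II, section 5 of the protocol says "All patients who are admitted to one of the participating hospitals and who have a CRAB isolated in a clinical culture will be included". Site is on file, since SAP 5 tabulates enrollment by site within region. Neither document says why site was left out of these weights or plans a site-adjusted sensitivity analysis for this contrast.

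**The concern.** Region is a coarse stand-in for hospital. If hospitals in one region differ both in the share of CRAB cultures counted as infection and in recorded mortality, region weights leave that difference in the contrast.

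The SAP's own coding rules offer one route. Under SAP 3.2, a culture lacking the information needed for classification is counted as colonized, and an admission not recorded as dead is counted as alive. A hospital with thin records would shift patients to colonized and deaths to alive together. That would create an apparent excess of mortality with infection.

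For respiratory isolates there is a second possible route to differing infection shares, because status follows the diagnosis entered at the site: "respiratory isolates are considered to be infected if the respiratory diagnosis on the CRF was tracheobronchitis, pneumonia, no mechanical ventilation, ventilator-associated pneumonia".

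At stake is the mortality and DOOR difference attributed to infection, in a study meant to inform trial design. Unlike region, infection status varies within a hospital, so a within-site comparison is possible.

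**Working it through.** The plan states no effect size, power or bias for this contrast, so there is no figure to reproduce.

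**Inputs from the documents.** About 2000 unique admissions before SAP exclusions (Protocol Appendix II, 7.1); two-sided 0.05 (SAP 3.1); the coding rules (SAP 3.2). Site counts, infection shares, mortality gaps and correlations are assumptions. Pooled mortality is assumed to be 25%, within the 16%-58% range for 30-day mortality in the Appendix II background.

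**1. Closed form.** Take one region with two site types of equal size, infection shares p1 and p2, a mortality gap d between the types, and no true difference within a site. Region weights do nothing inside one region, so

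bias = d × [p1/(p1+p2) − (1−p1)/((1−p1)+(1−p2))].

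Example: p1 = 0.7, p2 = 0.4, d = 10 points gives 10 × (0.7/1.1 − 0.3/0.9) = 10 × 0.303 = 3.0 points.

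| Infection shares | d = 5 | d = 10 | d = 20 |
|---|---|---|---|
| 60% vs 50% | 0.5 | 1.0 | 2.0 |
| 70% vs 40% | 1.5 | 3.0 | 6.1 |
| 80% vs 30% | 2.5 | 5.1 | 10.1 |

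Entries are percentage points. The sign reverses if high-infection sites have lower mortality. Bias is zero if either factor is equal across sites.

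**2. False positives.** With N = 2000, n1 = 2000 × (0.7+0.4)/2 = 1100 and n0 = 900. SE = √[0.25 × 0.75 × (1/1100 + 1/900)] = 1.95 points. For 70% vs 40% and d = 10 the shift is 3.03/1.95 = 1.56 SE, and the rejection rate is 1 − Φ(1.96 − 1.56) + Φ(−1.96 − 1.56) ≈ 34%. For 60/50 and 80/30 it is 8% and 74%. At N = 1000 the three rates are 7%, 20% and 45%.

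**3. Coding route alone.** Assume 60% infected and 30% mortality, with half the sites miscoding 20% of infections as colonized and missing 20% of deaths. Then p1 = 0.60, p2 = 0.48 and d = 30 × 0.20 = 6 points. Bias = 6 × (0.60/1.08 − 0.40/0.92) = 6 × 0.121 = 0.7 points. At 40% and 40% it is 12 × (0.60/0.96 − 0.40/1.04) = 2.9 points.

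**4. Simulation, region-only weights, true difference zero.**

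- 40 sites of about 27 admissions, 5 regions, site SD on the logit scale 0.7 (infection) and 0.5 (mortality), 30% of each variance between regions, 1500 runs. Correlation ±0.3: bias +0.95/−0.90 points, false positives 7%, coverage 93%. Correlation ±0.5: +1.62/−1.65 points, about 10%, coverage about 90%. Repeats with 400 runs each gave 1.0 to 1.3 points at +0.3 and 1.7 to 2.1 (in size) at ±0.5.
- 2000 admissions, 4 regions, 20 or 40 sites, SD 0.6 and 0.4, 600 runs. Correlation 0.5: 1.5 to 1.9 points, 15-16% false positives. Correlation −0.5: about −1.7 points, 16%. Correlation 0: between −0.2 and +0.1 points.

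**5. Candidate remedies.** 40 sites of 27, with one patient covariate related to infection and death:

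| Estimate | Bias, points |
|---|---|
| Region-only weights, correlation 0.5 | 1.9 |
| Region plus random site intercept, correlation 0.5 | 0.9 |
| Site-only Mantel-Haenszel, correlation 0 | about 2 |
| Site terms plus patient covariate, every correlation tried | 0.3 or less |

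The last row had an SD at most about 9% larger. The random intercept falls short because shrinkage pulls the site terms together: 0.9/1.9 = 47% of the bias remains. Without the patient covariate, and with the intercept replacing region, 1.1 of 2.1 points remained (52%). The Mantel-Haenszel estimate fails for a different reason: it ignores the patient covariate.

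**The case against.** The strongest objection is that bias is possible but not shown. It needs infection share and mortality to be correlated across hospitals, within region, after the other three covariates. The documents report neither quantity by site. This stands. A reader might infer that the planned contrast is biased, or biased in a known direction; neither follows. That routine culturing of ventilated patients masks an infection effect is only a hypothesis. Severity differences between patients in one hospital would also survive any site adjustment.

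The size is modest: at correlation 0.3 the bias is about 0.9 points against a standard error of about 2.6. This also stands for those assumptions.

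A reader might take the random site effect in the mortality model as an admission that site confounds this contrast. It is routine handling of clustering in a post hoc model, and shows only that the plan allows mortality to differ by hospital. Nor does infection status depend on the recorded diagnosis throughout. That rule covers respiratory isolates, while Protocol 6.3 counts blood and other sterile-site isolates as infection and uses surveillance criteria for urine and surgical wounds.

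What the objection does not remove is the omission. No other section adjusts this contrast for hospital, and the planned output could not reveal the problem if it existed.

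**Conclusion.** The omission is real and the harm is conditional. Without site in the weights, the infection vs colonization contrast can be biased in either direction. Under the simulated site variation, correlations of 0.3 to 0.5 give about 1 to 2 percentage points, with false positives of 7% to 16% against a nominal 5%. Larger figures need the more extreme site contrasts in the closed-form table. With no correlation there is no material bias.

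Two extensions should not be inferred. The primary objective in SAP 2.4.1, 30-day mortality of CRAB infections, does not rest on this contrast. The regional comparisons are a different matter, because site is nested in region there and cannot be handled in the same way.

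**What to change.** In SAP 5.2, add site to the propensity model for infection vs non-infection and keep immunocompromise, home origin and age-adjusted Charlson. Use site fixed effects, with small or single-group sites pooled within region by a stated rule. Region is then carried by the site terms. One set of weights serves 30-day mortality, 90-day mortality and the DOOR probability.

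Alternatively, keep the planned weights and report beside them, for the same three outcomes, a within-site estimate that also adjusts for those patient covariates.

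In either case, name the site-and-covariate-adjusted estimate in advance as the one to interpret. If results have already been seen, which the past tense of SAP 5.2 leaves open, label the addition post hoc. Do not rely on a random site intercept alone, and do not rest the conclusion on a site-only Mantel-Haenszel estimate.

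The wording on modeling also needs reconciling: SAP 3.1 limits it to infected subjects, while SAP 2.2 lists IPW DOOR under modeling and SAP 5.2 weights a contrast that includes colonized subjects.

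Cost: SAP text and one model on data already held. The CI may be slightly wider (SD up to about 9% larger in simulation). Sites with only one group contribute nothing unless pooled. That was under 0.2% of patients in simulations with 2000 admissions at 20 to 40 sites, but very small sites would raise it.
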